Participants will be told their treatment condition at Call 2, set a target quit date (TQD), and instructed how to use their study medications. Medications will be mailed following this call, along with a handout that describes: 1) when to begin taking study medication; 2) the type and doses involved; 3) how and when to obtain the next month's medication; and 4) complete instructions on proper medication use, including information from the package insert and contact information if they have questions regarding their medication and/or symptoms they experience. Participants will be mailed all Preparation Medication as well as one month of post-quit study medication after Call 2. They will need to call in to a study line to request that more medication be mailed to them (Standard Duration participants will call one time to receive their final 2 months of medication; Extended Duration participants will call once to get 2 additional months of medication and again to get the remaining 3 months of study medication). Participants will also receive a counseling handout with their medications; those randomized to intensive counseling will receive a Quit Plan listing their target quit day and when they start the medications and those randomized to minimal counseling will receive the mHealth handout.

Medication Type: Varenicline vs. C-NRT. Half of participants will be assigned to receive varenicline and half to receive nicotine patch + mini-lozenge (C-NRT). Unless participants are assigned to Preparation or Extended Duration, they will receive the standard dosing and duration of pharmacotherapy (e.g., 12 weeks of varenicline starting 1 week prequit or 12 weeks of C-NRT starting on the TQD; see Table 2).

Preparation

Medication: 4 weeks vs. Standard. Half of participants will be assigned to receive the Preparation Medication ("ON" condition); they will be instructed to use their assigned medication type (varenicline or nicotine patch) for 4 weeks prior to their TQD (see Table 2). Participants will use a lower dose of NRT (14-mg patches) while they are still smoking to reduce the risk of adverse events. Our prior research found no significant increases in adverse events among smokers who used NRT prior to the TQD and prior research has shown that use of

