Primary Aim 2: To identify two optimized smoking cessation treatments: one for varenicline and one for C-NRT. Data on both the 12-month abstinence effect sizes and costs of the different intervention components and combinations of components will be examined and multiple criteria decision analysis will be used to determine how to use each medication so that it is highly effective and but low in cost.

Secondary Aims: To determine: 1) whether person factors (e.g., sex, dependence, psychiatric history) moderate response to different treatment strategies; and 2) which proximal effects of each treatment factor mediate its long-term benefits; and 3) the main and interactive effects of the cessation interventions on cost-effectiveness and the cost-effectiveness of the optimal combinations of components for each medication type.

Implementation Challenges: Pandemic and Varenicline

Study recruitment began in November 2020.

In June 2021 Pfizer found that some lots of varenicline contained elevated levels of a novel nitrosamine that exceeded the level thought to be safe by the FDA for traditional nitrosamines. Therefore, we briefly paused recruitment. When we resumed recruitment, all participants were randomized to the C-NRT level of the Medication Type factor until November 2021 when we received IRB approval to use FDA-approved generic varenicline. When we were able to procure FDA approved varenicline, we changed our randomization ratio on this factor to 2:1 varenicline to C-NRT. When FDA initiated the varenicline recall, there were 42 participants actively taking

varenicline; 26 participants opted to switch to C-NRT and 16 stopped all medication. These 42 participants will not be included in the main outcome analyses.

We experienced significant implementation challenges with collecting in-person breath samples for biochemical verification of abstinence. In September 2023 we transitioned from using exhaled CO to verify abstinence ($\text{CO} < 6\text{ppm}$) to using cotinine assays on mailed saliva samples to verify abstinence ($\text{cotinine} \leq 10\text{ng/mL}$).

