Due to delays in implementing the study, and subsequent costs, caused by the global COVID pandemic, we were not able to reach our target sample size of 608. Preliminary data analyses conducted with data collected through December 7, 2023 indicated that there was only one factor that appeared to have a strong main effect for 6-month ($n=432$) and 12-month abstinence ($n=334$). The difference in abstinence rates for the two levels of each of the other 3 factors ranged from 0.0 to 4.9 percentage points. Given the lack of financial resources and the limited signal for additional main effects, we opted to close study recruitment at 538 (88.5% of the sample).

Sample Description

Participants' demographic and baseline smoking characteristics will be summarized using the appropriate descriptive statistics. The 42 people who were assigned varenicline and then discontinued varenicline and were switched to NRT after the FDA recalled Pfizer's varenicline will not be included in the main outcome analyses. We will conduct descriptive analyses to examine the differences between those in the varenicline condition who completed the treatment vs. those who switched to NRT during the FDA recall.

Outcome Analyses

Primary Aim 1: Identifying Main and Interactive Effects on Abstinence. The primary outcome is biochemically confirmed, point-prevalence abstinence (PPA) at 12-months post-TQD (based on $\text{CO} < 6\text{ ppm}$ for those assessed prior to September 2023 or salivary cotinine $\leq 10\text{ng/mL}$ for those assessed from September 2023 onward). We will conduct logistic regression analyses with predictors corresponding to the four factors using effect coding. The logistic regression models will include main and all interactive effects. Main effects will reflect the degree to which participants in the "ON" condition of a factor have significantly higher 1-year point-prevalence abstinence, relative to participants in the "OFF" condition for each factor, averaged across the other factors. These analyses will allow us to identify optimized treatments based upon main effects and interactions as they provide effect sizes (standardized regression coefficients) for the various intervention components and their combinations. We will conduct sensitivity analyses that compute abstinence means for those with CO vs. cotinine bio-verification. Due to the small sample sizes we will not do inferential testing on these comparisons.

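### The unadjusted varenicline versus C-NRT main effect pools three allocation ratios and two verification methods, so it is partly confounded with calendar period and assay; size and direction are unknown

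*SAP*

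**What the plan says.** **Allocation.** The protocol (Interventions, Medication Type) states: "Half of participants will be assigned to receive varenicline and half to receive nicotine patch + mini-lozenge (C-NRT". The SAP (Implementation Challenges) reports that after the 2021 recruitment pause "all participants were randomized to the C-NRT level of the Medication Type factor until November 2021", and that once generic varenicline was available "we changed our randomization ratio on this factor to 2:1 varenicline to C-NRT". It gives no end date for the 2:1 ratio and no enrolment by phase.

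**Exclusions.** At the recall 42 participants were taking varenicline; 26 moved to C-NRT and 16 stopped medication. "These 42 participants will not be included in the main outcome analyses".

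**Verification.** "In September 2023 we transitioned from using exhaled CO to verify abstinence" to salivary cotinine. The method follows the date of assessment.

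**Model.** The SAP (Primary Aim 1) fits a logistic regression with the four effect-coded factors and all their interactions, first without covariates. The secondary adjusted models name household smoking, sex, age, clinic, health system, other tobacco use, cigarettes per day and education. For verification method the SAP plans abstinence means for CO and for cotinine: "Due to the small sample sizes we will not do inferential testing on these comparisons".

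**Size and timing.** Recruitment closed at 538 after a look at the outcome data: "Preliminary data analyses conducted with data collected through December 7, 2023 indicated that there was only one factor" with a strong main effect. The SAP does not name that factor.

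**The concern.** When the allocation ratio changes over time, randomisation no longer balances the two drugs across calendar time. Most varenicline participants will come from the 2:1 phase, while many C-NRT participants will come from the two earlier phases. The exclusions widen this gap, because all 42 were varenicline participants from the first phase. The assay change lies along the same axis.

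Any difference in confirmed abstinence between phases, or between CO and cotinine, then enters the pooled varenicline versus C-NRT estimate. Its sign is open. Breath samples that could not be collected count as smoking and lower CO-confirmed rates. Unreturned saliva kits, and cotinine from other nicotine sources, lower cotinine-confirmed rates. These effects may partly cancel.

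Comparing the two drugs is a stated goal (protocol, Study Design), and Medication Type is one of the four Aim 1 main effects. Cross-drug comparisons of cost per quit use the same outcome. The protocol bases optimisation on effect size rather than significance, so a shift in percentage points is the relevant measure.

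**Working it through.** **1. The plan's own power figure.** Inputs (protocol, Sample Size): 304 per level, alpha .05, taken as two-sided. Power = Φ[(d − 1.96·SE0)/SE1], with pooled variance in SE0.
- 15% vs 25%: SE0 = √(.20×.80×2/304) = .0324; SE1 = √[(.15×.85 + .25×.75)/304] = .0322; power = Φ(1.13) = .871 (stated .87).
- 20% vs 30%: .814 (stated .81).

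The stated power is correct for the balanced design of 608.

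**2. Who gets cotinine.** The longest lag from randomisation to quit date is 5 weeks (protocol, Table 1 note), so the 12-month assessment falls at most 57 weeks after randomisation. Someone randomised on 30 November 2021 is due by about 3 January 2023, before September 2023. Counting 57 weeks back from 1 September 2023 gives late July 2022. On-schedule cotinine outcomes therefore arise only in the 2:1 phase.

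**3. Number verified by cotinine.** 538 − 334 = 204 had no 12-month outcome by 7 December 2023. The 6- and 12-month counts differ by 432 − 334 = 98, or about 16 a month, which adds up to about 52 for September to 7 December. The range is 204-256, or 162-214 if the 334 already omits the 42.

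**4. Assumed phase sizes (not in the documents).** 90-150 at 1:1, 20-80 C-NRT only, the rest of 538 at 2:1 to the end, with the 42 removed from 1:1 varenicline. The lower bound follows from 42 on varenicline at the recall, which implies about 84 at 1:1.

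Example with 100 / 50 / 388:

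| | 1:1 | C-NRT only | 2:1 | Total | Share from 2:1 |
|---|---|---|---|---|---|
| Varenicline | 50 − 42 = 8 | 0 | 258.7 | 266.7 | .970 |
| C-NRT | 50 | 50 | 129.3 | 229.3 | .564 |

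- Shift from a period difference = difference × (.970 − .564). At 5 points: 5 × .406 = 2.0 points.
- Shift from an assay gap, with 256 on cotinine split 2:1: cotinine shares are 170.7/266.7 = .640 and 85.3/229.3 = .372. At 5 points: 5 × .268 = 1.3 points.

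**5. Over the assumed range:**

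| Quantity | Result |
|---|---|
| Varenicline from the 2:1 phase | 86-99% |
| C-NRT from the 2:1 phase | 40-69% |
| Shift, 5-point CO-cotinine gap | 0.6-1.9 points |
| Shift, 5-point difference, 2:1 vs earlier phases | 1.5-2.5 points |

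Both shifts scale with the assumed difference.

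**6. Accrual check.** The 1.9 comes from 150 / 80 / 308 with 256 on cotinine. That leaves 308 − 256 = 52 CO-verified in the 2:1 phase over about nine months of quit dates (December 2021 to August 2022), against 9 × 98/6 = 147 at the implied rate. Splits that leave about 130-155 there (with 256 or 214 on cotinine) give about 0.9-1.5 points.

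**7. Other effects.** No allocation change is reported for the other three factors, so they stay balanced within each phase. In simulations of the full 15-effect model with no true drug effect and an assay gap common to both drugs, the rejection rate was .048-.056 for Preparation and .047-.058 for Type × Preparation, close to .05.

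**The case against.** The strongest reply has four parts.

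- **Disclosure and checks.** The SAP reports every allocation change and the assay switch. It plans CO and cotinine means, and it analyses self-reported abstinence at Weeks 12 and 26, which no assay affects. This helps but does not close the gap. The means have no stated split by drug or period, self-report stops short of the 12-month endpoint, and self-report does not remove calendar period.
- **Reason for not adjusting.** The SAP wants effects in diverse smokers, and its covariate list may not be exhaustive. But allocation period is part of how treatment was assigned, not a smoker characteristic, so that reason does not cover it. A list that could be extended is not a plan to extend it.
- **No evidence of a difference.** The documents show neither a time trend in abstinence nor a CO-cotinine gap. This stands, and it is why no size or direction can be claimed.
- **Limited consequence.** In the 5-point illustrations the shift is at most about 2.5 points, against the 10-point difference the protocol calls clinically significant. The protocol says a strong drug effect would mark the preferred basis for treatment, but the SAP omits that sentence and keeps one package per drug. This also stands.

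A reader might infer that the drug comparison is invalid, or that the strong factor in the December 2023 look was Medication Type and is an artefact. The documents support neither. Both drugs ran concurrently in two of the three phases, and the factor is not named.

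**Conclusion.** The concern holds for one contrast, the varenicline versus C-NRT main effect. Its association with allocation period and verification method follows from the documented conduct of the trial, and neither the primary model nor the named secondary covariates address it. The imbalance is certain; a material bias is not.

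The illustrated shifts rest on assumed phase sizes, on the 42 being counted in the 538, and on the 2:1 ratio lasting to the end of recruitment. An earlier return to 1:1 would change the shares. The upper end of the assay range also needs uneven accrual. Within-drug selection of components is not at stake.

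**What to change.** For the Medication Type contrast only, keep the planned unadjusted result and report beside it:

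1. The same model with allocation period added (three levels, by randomisation date).
2. A table of enrolment and 12-month confirmed abstinence by period, verification method and drug, with Week 52 self-reported 7-day abstinence by drug. The protocol (Calls 7-10) already collects this self-report.

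Base any statement that one drug is better on the period-adjusted estimate. State that a period term does not remove an assay effect that differs by drug. Label these analyses as added after the December 2023 data look.

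An analysis of the 2:1 phase alone, with the four main effects, may be shown as a descriptive check. It leaves out the few first-phase varenicline participants who remain after the exclusions (3-33 in the illustration). C-NRT would have only about 13-18 people per cell there, too few for the full 15-effect model.

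The cost is SAP wording, one model and one table from data already held, plus some power. With Mantel-Haenszel weights nV·nC/(nV + nC) per phase, the C-NRT-only phase has weight zero. Power for 15% vs 25% then falls from about .78-.80 pooled to about .62-.74 in the illustration. The C-NRT-only participants still inform the other three factors.

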The question of primary interest is how treatments affect abstinence amongst diverse smokers amidst the variety of other factors that also influence smokers' ability to maintain abstinence, not whether such effects occur in a statistically adjusted sample. Therefore, the primary analyses will first be conducted without covariate adjustment, to ensure that covariate adjustment does not cloud interpretation or reduce external validity for various reasons. In secondary analyses, we will statistically control for covariates including: living with a smoker, biological sex, age, clinic, health system, use of other tobacco products at baseline, cigarettes per day at baseline,

and education. In addition, primary analyses will exclude participants who were switched to cNRT from varenicline or stopped using any medication during the FDA varenicline recall.

Self-reported point-prevalence abstinence at Weeks 12 and 26 and biochemically confirmed abstinence at Week 26 will be analyzed as secondary outcomes using methods similar to those used for the primary outcome. These analyses will allow us to examine the stability or robustness of the intervention component effects.

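### The SAP drops 42 randomised varenicline participants from the primary analysis and states no as-randomised analysis of the factor effects beside it

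*SAP*

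**What the plan says.** The SAP section on implementation challenges reports: "When FDA initiated the varenicline recall, there were 42 participants actively taking" varenicline, of whom "26 participants opted to switch to C-NRT and 16 stopped all medication". It then says: "These 42 participants will not be included in the main outcome analyses". The Sample Description repeats the exclusion, and Outcome Analyses, Primary Aim 1, states that "primary analyses will exclude participants who were switched to cNRT from varenicline or stopped using any medication during the FDA varenicline recall".

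For 12-month confirmed abstinence the SAP states three things: an unadjusted logistic model with all main effects and interactions, a covariate-adjusted secondary version, and a comparison of abstinence means by CO or cotinine verification without inference. For the excluded group it plans only a descriptive comparison of "those in the varenicline condition who completed the treatment vs. those who switched to NRT during the FDA recall". The term intent-to-treat appears once in the SAP, for the abstinence outcome used in cost per quit.

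On allocation, the same section says that after the pause "all participants were randomized to the C-NRT level of the Medication Type factor until November 2021" and that later "we changed our randomization ratio on this factor to 2:1 varenicline to C-NRT". The protocol's Interventions section describes a half-and-half split.

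In the protocol, randomisation takes place at the second study call and medication is mailed after it. The protocol has no recall exclusion, and its sample size section counts all 608 participants, with missing outcomes treated as smoking.

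**The concern.** Being on varenicline on the day of the recall is not a baseline characteristic. It depends on whether the person had persisted with the drug, and on the course length set by the assigned Duration and Preparation levels. It cannot occur at the C-NRT level. C-NRT participants from the same months stay in, and so do varenicline participants who had already stopped or finished. The analysed varenicline group is therefore no longer the group that was randomised.

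Both documents choose components from estimated effect sizes, and the protocol says this is done in preference to significance. A shift of a point or two therefore enters the results directly. With no as-randomised result beside the primary one, a reader cannot see how much the exclusion contributes.

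A second, separate feature touches the same contrast. Allocation went from the original split to C-NRT only and then to 2:1, so Medication Type is partly mixed with calendar time. The SAP's covariate list has no date or period term.

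**Working it through.** **Reproducing the plan's power.** Two-proportion normal approximation, pooled null variance, two-sided 0.05 (sidedness is not stated), 304 per level: 0.871 for 15% vs 25% and 0.814 for 20% vs 30%. The protocol states .87 and .81, so this formula is used below.

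**Counts.** 26 + 16 = 42. 538/608 = 88.5%. 42/538 = 7.8%, assuming the 42 are among the 538.

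**Size of the varenicline level (not given).** Assume V0 = 50-100 per Medication Type level before the recall, M = 20-100 in the C-NRT-only period, and 2:1 afterwards. Then N2 = 538 - 2·V0 - M, V = V0 + (2/3)·N2 and C = 538 - V.

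| V0 | M | N2 | V | C | 42/V | Shift per 10-point gap (420/V) |
|---|---|---|---|---|---|---|
| 50 | 20 | 418 | 329 | 209 | 12.8% | 1.28 |
| 50 | 100 | 338 | 275 | 263 | 15.3% | 1.53 |
| 100 | 20 | 318 | 312 | 226 | 13.5% | 1.35 |
| 100 | 100 | 238 | 259 | 279 | 16.2% | 1.62 |

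**Direction.** If people who stay on the drug quit more often (assumption), removing them lowers the varenicline rate. But the 42 then lost varenicline, which could make their own rate low, and removing them would raise it. Illustration with 269 C-NRT and 227 + 42 varenicline, where the analysed contrast is 20% vs 30%: the as-randomised difference is (227 × 0.30 + 42 × p)/269 - 0.20. For p = 10%, 20%, 30% and 40% this is 6.9, 8.4, 10.0 and 11.6 points. The documents do not give p.

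**Link with the other factors.** Protocol Table 2 implies varenicline courses of about 12 and 16 weeks (Standard) and 24 and 28 weeks (Extended), 80 in sum. With even enrolment and full adherence (assumptions), 42 × 52/80 = about 27 of the 42 would be Extended and 15 Standard. This is a reason to tabulate them.

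**Dilution in the as-assigned model.** If the 42 quit at the C-NRT rate, a true 10 points becomes 10 × (V - 42)/V = 8.4-8.7. Power is about 0.70 (15% base) or 0.63 (20% base). With the exclusion and the full 10 points it is 0.78-0.80 or 0.72-0.73.

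**Allocation period.** Early means randomised before the 2:1 period. The early share is (V0 + M)/C for C-NRT. For varenicline it is V0/V with the 42 and (V0 - 42)/(V - 42) without them. Assume a 5-point early-versus-late difference in abstinence; the contrast then moves by 5 × the difference in shares.

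| V0, M | C-NRT | Varenicline, with 42 | Varenicline, without | Shift with | Shift without |
|---|---|---|---|---|---|
| 50, 20 | 0.33 | 0.15 | 0.03 | 0.9 | 1.5 |
| 50, 100 | 0.57 | 0.18 | 0.03 | 2.0 | 2.7 |
| 100, 20 | 0.53 | 0.32 | 0.21 | 1.1 | 1.6 |
| 100, 100 | 0.72 | 0.39 | 0.27 | 1.7 | 2.2 |

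**Cost of the period term.** The C-NRT-only stratum carries no information on Medication Type. The information left is V0/2 + 2·N2/9, the diluted effect is 7.9-8.3 points, and power is 0.52-0.64 (15% base) or 0.46-0.56 (20% base).

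**The case against.** The recall was external, the exclusion is stated openly, and a reader may reasonably want the effect of varenicline when it could actually be supplied. That stands: the exclusion is acceptable as the primary choice.

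The SAP limits the exclusion to main or primary analyses and uses intent-to-treat abstinence for cost per quit, so other analyses may include the 42. This stands only in part. No such factor-effect analysis is stated, and the cost-per-quit text does not say whether the 42 are in.

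The magnitudes rest on assumed arm sizes and rates. That also stands. They are illustrations, and a pre-recall varenicline group above 100 cannot be ruled out. The gap in the text does not depend on them.

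Four stronger readings are tempting but not supported:

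- A reader might infer that the exclusion biases the result towards varenicline. The outcomes of the 42 are not given and the two mechanisms pull in opposite directions.
- A reader might infer that the Medication Type estimate will pick the preferred drug. The protocol has a sentence to that effect, but the SAP does not carry it, and both documents decide beforehand on one package per drug.
- A reader might infer that the 16 who stopped all medication are left out of the descriptive comparison. The Sample Description loosely calls all 42 switched, so the wording is ambiguous rather than a clear omission.
- A reader might count the power lost by closing recruitment at 538, or the calendar mixing, as effects of the exclusion. The first is a separate decision; the second exists even if nobody is excluded.

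**Conclusion.** The point holds as a missing sensitivity analysis, not as a fault that invalidates the primary result. The primary analysis removes 42 randomised participants by a state that arises after randomisation and can occur at one Medication Type level only. Nothing stated in the SAP shows the factor effects without that removal.

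The bias is probably modest: 1.3-1.6 points on the varenicline rate per 10-point gap, against a 10-point design difference. This assumes that the 42 are among the 538 and that the varenicline level is about 260-330.

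The allocation-period point is related but stands alone. With an assumed 5-point early-versus-late difference and 50-100 varenicline participants before the recall, the unadjusted contrast moves by about 0.9-2.0 points with the 42 included and 1.5-2.7 without them.

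Confidence is high that the text has these gaps and lower on their size. Both are worth closing because this needs no new data.

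**What to change.** 1. Keep the exclusion analysis as primary and say which question it answers.
2. Add, reported beside it, the same logistic model in all randomised participants as assigned, with missing outcomes counted as smoking. Read it by its estimate and confidence interval.
3. Tabulate the 42 by all four factors.
4. Reconcile the Sample Description (switched to NRT) with the implementation section (26 switched, 16 stopped) so that the descriptive comparison clearly covers all 42.
5. State whether the intent-to-treat population for cost per quit includes the 42.
6. As a separate sensitivity analysis, report the Medication Type effect and its interactions with a three-level allocation-period term (original allocation, C-NRT only, 2:1).

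The cost is SAP wording, one extra model run without and with the period term, and one table, all on existing data. The statistical price is the dilution and lower power shown above, and the period term costs more than the as-assigned run. Neither run should replace the primary analysis, and a non-significant result in either should not be read as overturning it.

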Additional Exploratory Analyses. Seven-day point-prevalence abstinence at Weeks 12 and 26 will be analyzed using similar methods to those used for the primary outcome. These analyses will allow us to examine the stability or robustness of the intervention component effects. These findings may also be used in future research to optimize cessation treatments based on longer-term outcomes. In addition, we will examine the occurrence of adverse events and its relation with adherence. Logistic and linear regression will be used for categorical and continuous variables, respectively, with appropriate transformations of continuous variables and/or adoption of generalized regression modeling techniques as necessary. Analyses of these exploratory outcomes will achieve **scientific rigor** by controlling for experiment-wise error in families of related tests using the Benjamini-Hochberg approach¹⁴⁸⁻¹⁵⁰.

Sample Size and Power Considerations

This study was designed to have sufficient power to detect a clinically significant (i.e., 10 percentage point increase) difference between the two levels of a factor (i.e., the main effects) in 52-week biochemically confirmed abstinence. In other words, the sample size was chosen to ensure that the Primary Aim comparisons of ON vs OFF levels of a factor would have sufficient power to detect clinically meaningful increases in abstinence. It should also be noted that because this is a balanced factorial design, we will have the same power to detect 2-way interactions that we have to detect main effects. To address the Primary Aim, we assume that the base rate (participants who get Standard Preparation Medication and Standard Duration) of 52-week biochemically confirmed abstinence will be 20%. This is consistent with our prior research that found a self-reported 52-week abstinence rate of 26.8% among primary care smokers who received 8 weeks of C-NRT¹³ and our efficacy trial that showed biochemically confirmed 52-week abstinence rates of approximately 20% for smokers who received either 12 weeks of varenicline or 12 weeks of C-NRT⁴³. If we assume that abstinence rates among real-world primary care patients might be somewhat lower (e.g., 15%), then with a sample size of

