608 (304 in the ON and 304 in the OFF levels of each factor with no missing data because missing=smoking) and $\alpha=.05$, we are powered at .87 to detect a difference between 15% and 25% in 52-week biochemically confirmed abstinence; we also have sufficient power (.81) to detect a difference between 20% and 30% in 52-week biochemically confirmed abstinence. Treatment optimization will be based on the effect size estimates of the main and interactive effects on 12-month abstinence, rather than statistical significance, consistent with our prior research¹⁵.

Protection of Human Subjects

Human Subjects Involvement and Characteristics. All EHR-identified smokers in a clinic will receive an invitation (in their preferred modality: mail, MyChart messages from the EHR, text) to find out more about smoking treatment by calling a healthcare system Care Manager. In addition, Medical Assistants (MAs), using an EHR-guided prompt, will inform all smokers attending in-person or tele-health visits that they will be getting a call from their clinic’s Care Manager, using an opt-out approach. The Care Manager will call the smoker and assess their interest in quitting smoking. Smokers who are interested in quitting in the next 30 days will be offered a variety of cessation treatment options, including the opportunity to participate in this smoking cessation study.

Specific eligibility requirements for this project are: age >17 years; smoking >4 cigarettes/day for the previous 6 months; able to read, write, and speak English; not currently taking bupropion or varenicline; if currently using NRT, agreeing to use only study medication for the duration of the study; medically eligible to use study medications (e.g., no severe renal disease, no allergic reactions to tested agents); and, if the participant is a woman of childbearing potential, using an approved method of birth control during treatment.

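### The stated power (.87/.81) is for 608 participants; with 538 recruited and 42 excluded, power for 20% vs 30% is about .73 to .77, and the SAP gives no updated figure

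*SAP*

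**What the plan says.** Protocol, Sample Size and Power Considerations: the study is sized to detect a 10-percentage-point main effect on biochemically confirmed abstinence at 52 weeks. Its planning assumption reads "we assume that the base rate (participants who get Standard Preparation Medication and Standard Duration) of 52-week biochemically confirmed abstinence will be 20" per cent, with 15% considered as a lower real-world rate. With 608 participants, 304 at each level of each factor, alpha .05 and missing counted as smoking, power is .87 for 15% vs 25%, and "we also have sufficient power (.81) to detect a difference between 20% and 30% in 52-week biochemically confirmed abstinence".

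SAP, Implementation Challenges: the target of 608 was not reached, and "we opted to close study recruitment at 538 (88.5% of the sample". Of the varenicline participants on drug at the recall, 26 switched to C-NRT and 16 stopped all medication. "These 42 participants will not be included in the main outcome analyses". The Primary Aim 1 section repeats this: "primary analyses will exclude participants who were switched to cNRT from varenicline or stopped using any medication during the FDA varenicline recall". The same part of the SAP describes changed allocation on one factor. After the pause, "all participants were randomized to the C-NRT level of the Medication Type factor until November 2021", and then "we changed our randomization ratio on this factor to 2:1 varenicline to C-NRT". The final split is not given.

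SAP, Primary Aim 1, on the model: "The logistic regression models will include main and all interactive effects". The SAP's Study Overview still gives N=608, and the SAP contains no power statement of its own.

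**The concern.** The power on record rests on two conditions, 608 participants and equal levels. The first is not met, and the SAP's account of allocation puts the second in doubt for Medication Type. The SAP reports the smaller headcount but not what it does to power or precision.

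Primary Aim 1 asks which components have a statistically significant benefit and which significantly strengthen or weaken others, and the protocol says the sample size was chosen for those ON-versus-OFF comparisons. A reader who finds a non-significant main effect, and only .87/.81 to set it against, may take it as better evidence against a 10-point effect than it is. The SAP already reasons in this direction: it closed recruitment partly because differences for three factors were 0.0 to 4.9 points in preliminary data, with 334 participants at 12 months.

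**Working it through.** **Inputs.** From the protocol: 608 participants, 304 per level, alpha .05 (sidedness not stated; only a two-sided test reproduces the stated power), 15% vs 25% and 20% vs 30%. From the SAP: 538 recruited, 42 excluded. 538/608 = 88.5%, as stated. 538 − 42 = 496, or 248 per level if balanced. This assumes that the 42 are among the 538, which is the natural reading but is not stated, so both numbers are carried.

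**Step 1: the protocol's method.** Two-proportion comparison with pooled variance under the null, n per level:

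power = Φ{ [ |p2 − p1| − 1.96·√(2·p̄(1−p̄)/n) ] / √([p1(1−p1) + p2(1−p2)]/n) }

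- n = 304, 20% vs 30%: (0.10 − 1.96 × 0.03512)/0.03489 = 0.893, so power is .814. The protocol says .81.
- n = 304, 15% vs 25%: (0.10 − 1.96 × 0.03244)/0.03219 = 1.131, so power is .871. The protocol says .87.
- n = 248, 20% vs 30%: (0.10 − 1.96 × 0.03889)/0.03863 = 0.616, so power is .731.

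**Step 2: the planned model.** In the saturated 16-cell logistic model with effect coding, a main-effect coefficient is β = [logit(p2) − logit(p1)]/2. Its variance is the sum over cells of (1/16)²/[n·p(1−p)], with n the cell size. For 20% vs 30% at 496 with balanced cells (31 each): β = 0.2695, variance = (8/(256 × 31)) × (1/0.16 + 1/0.21) = 0.01110, SE = 0.1054, and Φ(0.2695/0.1054 − 1.96) = .725.

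| Analysed N (balanced) | Two-proportion, 15 vs 25 / 20 vs 30 | Planned model, 15 vs 25 / 20 vs 30 |
|---|---|---|
| 608 | .871 / .814 | .863 / .808 |
| 538 | .828 / .765 | .820 / .759 |
| 496 | .797 / .731 | .788 / .725 |

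Simulation of the saturated model at 496 with balanced cells (200,000 trials, 0.5 added to each cell count) gave .778/.718, close to the formula.

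For 80% power, 20% vs 30% needs 588 (two-proportion) or 596 (planned model), more than were recruited. 15% vs 25% needs 500 or 512.

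**Step 3: imbalance on Medication Type.** The split is not in the documents, so these varenicline/C-NRT splits of 496 are assumptions, with nV/8 in each varenicline cell and (496 − nV)/8 in each C-NRT cell. In the saturated model the other three factors also lose power, because each coefficient weights the 16 cells equally and the sparser half adds more variance.

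| Assumed split | Power for the other three factors, 15 vs 25 / 20 vs 30 |
|---|---|
| 220/276 | .783 / .720 |
| 200/296 | .772 / .709 |
| 180/316 | .756 / .691 |

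For Medication Type itself at 200/296, power is .788/.720 if varenicline does better and .758/.698 if C-NRT does better.

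**Step 4: precision.** The 95% half-width for a main effect is 1.96·√(4p(1−p)/N). At 496 and an assumed 20% overall abstinence it is 1.96·√(0.64/496) = 7.0 points (6.3 to 7.6 for 15% to 25%). For a difference-in-differences it doubles to 14.1 points. At the preliminary 12-month n of 334 the main-effect half-width is 1.96·√(0.64/334) = 8.6 points. If the observed 4.9 points was a 12-month difference, its upper limit would be about 4.9 + 8.6 = 13.5 points, which does not exclude 10.

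**The case against.** The strongest reply is that nothing is hidden and little changes. The SAP reports the missed target, the reasons, the 538, the 42 and the changed allocation. The protocol ties .87/.81 openly to 608 with 304 per level, so a careful reader can see that they have lapsed. Neither document sets .80 as a minimum. For 15% vs 25%, power stays at about .80 to .83, and from a 20% base the difference detectable at 80% power in the planned model moves only from 9.9 points at 608 to 11.0 at 496. The protocol bases optimization on effect sizes rather than significance. Recruitment is closed, so a new power figure changes no design decision. The splits in Step 3 are assumed, and even their direction is uncertain because the later 2:1 ratio favours varenicline.

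Much of this stands. The shortfall is moderate and disclosed, .80 is a convention, package selection does not turn on these tests, and the split figures only illustrate. It does not remove the point. The protocol names 20% as its base rate and calls .81 sufficient, and the trial falls short of .81 at either analysed number. Aim 1 is still framed in terms of significance, and effect-size decisions also need a stated precision. Nor is this a request for power at the observed effect: it is power for the prespecified 10-point difference at the number analysed.

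**Conclusion.** The concern holds. The protocol's power figures are right for 608 and no longer describe the trial, and the SAP does not replace them. Power for the protocol's main scenario, 20% vs 30%, falls from .81 to between .73 (496 analysed) and .77 (538 analysed). For 15% vs 25% it falls from .87 to between .80 and .83. The conclusion for 20% vs 30% does not depend on whether the 42 are among the 538. These values assume a two-sided 5% test and balanced levels; a clearly unequal Medication Type split would lower them further, to .69 for the other factors in the most unequal split tried. This should be corrected in the SAP. It does not undermine the design or the effect-size basis of optimization.

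**What to change.** In the SAP:

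1. State the analysed N and whether the 42 are among the 538. Give the power for a 10-point main effect at that N, computed for the planned saturated model with the actual cell sizes, and say that it supersedes the protocol's figures. With balanced cells this is about .79/.73 at 496, or .82/.76 at 538.
2. Say that non-significant main effects and interactions will be reported with 95% confidence intervals, main effects being read against the protocol's 10-point threshold, and will not be presented as evidence of no effect.

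A related clarification, not an error: the protocol's statement that 2-way interactions have the same power as main effects holds for an equal effect-coded coefficient in a balanced design, which corresponds to a difference-in-differences of about 20 points. For 10 points, a size the protocol does not name, power on the risk-difference scale is about .30 to .37 at 608 and .25 to .31 at 496. One sentence would prevent misreading.

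The cost is a few sentences. The study team already has the cell sizes, no new data are needed, and the protocol's section can stand as the planning record.
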